5.3. Repeated Measurements in Spirometry Data

If there are multiple valid assessments in spirometry data at a particular visit, the highest valid value will be chosen for analysis.

5.4. Absolute and Relative Change from Baseline

The absolute change from baseline at each post-baseline visit is calculated as (post-baseline value – Baseline), while the relative change (%) from baseline at each post-baseline visit is calculated as (post-baseline value – Baseline)/Baseline×100.

5.5. Missing Dates of AE and Prior and Concomitant Medications

5.5.1. Missing Date Information for Adverse Events

The following imputation rules only apply to cases in which the start date is incomplete (ie, partially missing) for adverse events.

Missing day and month

- If the year is same as the year of the date of the first dose of double-blind study drug, then the day and month of the date of the first dose of double-blind study drug will be assigned to the missing fields.
- If the year is prior to the year of the date of the first dose double-blind study drug, then December 31 will be assigned to the missing fields.
- If the year is after the year of the date of the first dose double-blind study drug, then January 1 will be assigned to the missing fields.

Missing month only

• The day will be treated as missing and both month and day will be replaced according to the above procedure.

Missing day only

- If the month and year are same as the year and month of the date of the first dose double-blind study drug, then the date of the first dose double-blind study drug will be assigned to the missing day.
- If either the year is before the year of the date of the first dose of double-blind study drug or if both years are the same but the month is before the month of the date of the first dose of double-blind study drug, then the last day of the month will be assigned to the missing day.
- If either the year is after the year of the date of the first dose of double-blind study drug or if both years are the same but the month is after the month of the date of the first dose of double-blind study drug, then the first day of the month will be assigned to the missing day.

If the stop date is complete and the imputed start date as above is after the stop date, the start date will be imputed by the stop date.

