4.2. Inclusion Criteria

Patients must meet all of the following conditions to be eligible for enrollment into the study:

- 1. Completion of study treatment (placebo or active) in the previous Phase 3, double-blind study protocol (Protocol PTC124-GD-021-CF).
- 2. Evidence of signed and dated informed consent/assent document(s) indicating that the patient (and/or his parent/legal guardian) has been informed of all pertinent aspects of the trial. *Note: If the study candidate is considered a child under local regulation, a parent or legal guardian must provide written consent prior to initiation of study screening procedures and the study candidate may be required to provide written assent. The rules of the responsible Institutional Review Board/Independent Ethic Committee (IRB/IEC) regarding whether one or both parents must provide consent and the appropriate ages for obtaining consent and assent from the patient should be followed.*
- 3. In patients who are sexually active, willingness to abstain from sexual intercourse or employ a barrier or medical method of contraception during the study drug administration and 4-week follow-up period.
- 4. Willingness and ability to comply with scheduled visits, ataluren administration plan, study procedures, laboratory tests, and study restrictions.

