11.4.5. Primary Variables

11.4.5.1 *Adverse Event*

Adverse events will be classified using the MedDRA classification system. The severity of adverse events will be graded according to the CTCAE, Version 3.0, whenever possible.

A treatment-emergent adverse event is defined as an adverse event that occurs or worsens in severity in the period extending from the day of a subject's first ataluren dose in this study to 4 weeks after the last ataluren dose in this study.

The number and percentage of subjects experiencing a specific adverse event will be tabulated by body system and MedDRA term. A subject having the same event more than once will be counted only once. Adverse events will be summarized by worst CTCAE grade within a subject. Exposure-adjusted incidence rate will be reported.

Adverse events classified as CTCAE Grade 3 or higher; study-drug-related events; hepatic, and renal events leading to special diagnostic evaluations; events leading to discontinuation from treatment; SAEs; and AESIs will be considered with special attention.

11.4.5.2 *Laboratory Data*

Hematological, serum biochemistry, urine data, and their changes (only for continuous laboratory parameters) from baseline will be summarized descriptively for each visit. Hematological, serum biochemistry, and urine data will be graded according to CTCAE severity grade when applicable. For parameters for which a CTCAE scale does not exist, the frequency of subjects with values below, within, and above the normal ranges will be summarized. Summary tables will be presented for each relevant assay to show the number of subjects by severity grade with corresponding percentages. Subjects will be characterized only once for a given assay, based on their worst severity grade observed during the time period of interest.

Separate listings and tables will be created for assessment of hepatic and renal parameters.

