2. STUDY OVERVIEW

2.1. Study Design

Study 021e is a Phase 3, international, multicenter, open-label, extension study of ataluren in patients with nmCF that have completed participation in the double-blind study PTC124-GD-021-CF (Study 021).

All eligible patients that completed participation in Study 021 will be enrolled into the study. Eligible subjects will receive oral ataluren administered 3 times per day (TID) at respective morning, midday, and evening doses of 10-, 10-, and 20-mg/kg for 96 weeks. The detailed schedule of assessments are displayed in Table 1.

Screening and baseline procedures are structured to avoid a gap in treatment between the double-blind study (PTC124-GD-021-CF) and this extension study. When possible, Screening/Baseline (Visit 1) for this extension study should occur on the same day as the End-of-Study visit for the double-blind study (PTC124-GD-021-CF). During the treatment period, study assessments will be performed at clinic visits at Week 12 and thereafter every 12 weeks until the end of the study.

Planned interim safety analyses will be conducted by an independent data monitoring committee (DMC). The first safety review will occur when ~ 100 patients have completed >=36 weeks of treatment. The second safety review will occur when ~ 100 patients have completed >=72 weeks of treatment.

The study will be terminated prematurely according to company's strategic decision on March 2, 2017. All subject who are on-going by then will be discontinued.

Table 1. Schedule of Events

| Study Period | Screening/B aseline | Treatment Period | | | | | | Post-Treatment | | |
|---|---------------------|------------------|----|----|----|----|----|----------------|-----------------------------|--------------------|
| Study Week (±7 days) | Day 1 | 12 | 24 | 36 | 48 | 60 | 72 | 84 | End of Tx/ Premature D/C 96 | 4 Weeks Post-Tx |
| Visit | 1 | 2 | 3 | 4 | 5 | 6 | 7 | 8 | 9 | 10 |
| Informed consent | X | | | | | | | | | |
| CFQ-R administration | X ^a | X | X | X | X | X | X | X | X | |
| Vital signs | Xa | X | X | X | X | X | X | X | X | X |
| Height | X ^a | X | X | X | X | X | X | X | X | X |
| Weight | X ^a | X | X | X | X | X | X | X | X | X |
| Physical examination | X ^a | | | | X | | | | X | X |
| Hematology | X ^a | X | X | X | X | X | X | X | X | X |
| Biochemistry | X ^a | X | X | X | X | X | X | X | X | X |
| Urinalysis | Xa | X | X | X | X | X | X | X | X | X |
| Renal ultrasound | Xa | | | | X | | | | X | |

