4.10.1. Adverse Events

Adverse events will be classified by System Organ Class (SOC) and Preferred Term (PT) using the Medical Dictionary for Regulatory Activities (MedDRA Version 17.0). In order to remain consistent in the adverse event data collected in previous trials, the severity of adverse events will be graded by the investigator according to the CTCAE, Version 3.0 whenever possible. The adverse event CTCAE/severity grades include Grade 1 (Mild), Grade 2 (Moderate), Grade 3 (Severe), Grade 4 (Life-threatening), and Grade 5 (Fatal). The relationship of study drug to adverse event has 4 categories: probable, possible, unlikely and unrelated.

A treatment-emergent adverse event (TEAE) is defined as an adverse event that occurs or worsens in the period extending from the day of a subject's first dose of study drug to 4 weeks after the last dose of study drug in this study. In the following analyses, a subject having the

PTC Therapeutics, Inc. – Confidential Page 12 of 24 Version 1.0 14JUL2017 same event more than once will be counted only once. Adverse events will be summarized by worst CTCAE/severity grade.

Total numbers of AEs, TEAEs and serious AEs (SAE) and the number and percentage of subjects experiencing ≥1 TEAE, ≥1 SAE, discontinuation due to AE, and death will be tabulated. The number and percentage of subjects with TEAEs and SAEs will be by Relationship to study drug and CTCAE/severity, respectively.

The number and percentage of subjects experiencing a specific TEAE will be tabulated

- 1) by SOC, and PT
- 2) by SOC, PT, and CTCAE/severity grade
- 3) by SOC in the descending order of the SOC frequency in ataluren group,
- 4) by PT in the descending order of the PT frequency in ataluren group.

The following TEAEs will be analyzed similarly:

- 1) by SOC, and PT and
- 2) by SOC, PT, and CTCAE/severity grade.
 - Possibly or probably treatment-related TEAEs
 - Serious TEAEs and possibly or probably treatment-related serious TEAEs
 - TEAEs leading to discontinuation from treatment
 - Adrenal, hepatic and renal TEAEs and possibly or probably treatment-related adrenal, hepatic and renal TEAEs leading to special diagnosis evaluation
 - TEAEs with CTCAE/severity grade ≥3 and possibly or probably treatment-related TEAEs with CTCAE/severity grade ≥3
 - Common TEAEs (subject frequency of $\geq 5\%$)

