5.5.2. Missing Date Information for Prior or Concomitant Medications

For prior or concomitant medications, including rescue medications, incomplete (ie, partial missing) start date and/or stop date will be imputed. When the start date and the stop date are both incomplete for a subject, impute the start date first.

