5.5.2.1. Incomplete Start Date

The following rules will be applied to impute the missing numerical fields. If the stop date is complete and the imputed start date is after the stop date, then the start date will be imputed using the stop date.

Missing day and month

- If the year of the incomplete start date is the same as the year of the date of the first dose of double-blind study drug, then the day and month of the date of the first dose of double-blind study drug will be assigned to the missing fields.
- If the year of the incomplete start date is prior to the year of the date of the first dose of double-blind study drug, then December 31 will be assigned to the missing fields.
- If the year of the incomplete start date is after the year of the date of the first dose of double-blind study drug, then January 1 will be assigned to the missing fields.

Missing month only

• The day will be treated as missing and both month and day will be replaced according to the above procedure.

Missing day only

- If the month and year of the incomplete start date are the same as the month and year of the date of the first dose of double-blind study drug, then the day of the date of the first dose of double-blind study drug will be assigned to the missing day.
- If either the year is before the year of the date of the first dose of double-blind study drug or if both years are the same but the month is before the month of the date of the first dose of double-blind study drug, then the last day of the month will be assigned to the missing day.
- If either the year is after the year of the date of the first dose of double-blind study drug or if both years are the same but the month is after the month of the date of the first dose of double-blind study drug, then the first day of the month will be assigned to the missing day.

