5.5.2.2. Incomplete Stop Date

The following rules will be applied to impute the missing numerical fields. If the date of the last dose of double-blind study drug is missing, replace it with the last visit date or data cut-off date if the subject is on-going. If the imputed stop date is before the start date (imputed or non-imputed start date), then the imputed stop date will be equal to the start date.

Missing day and month

- If the year of the incomplete stop date is the same as the year of the date of the last dose of double-blind study drug, then the day and month of the date of the last dose of double-blind study drug will be assigned to the missing fields.
- If the year of the incomplete stop date is prior to the year of the date of the last dose of double-blind study drug, then December 31 will be assigned to the missing fields.
- If the year of the incomplete stop date is after the year of the date of the last dose of double-blind study drug, then January 1 will be assigned to the missing fields.

Missing month only

• The day will be treated as missing and both month and day will be replaced according to the above procedure.

Missing day only

• If the month and year of the incomplete stop date are the same as the month and year of the date of the last dose of double-blind study drug, then the day of the date of the last dose of double-blind study drug will be assigned to the missing day.

• If either the year is before the year of the date of the last dose of double-blind study drug or if both years are the same but the month is before the month of the date of the last dose of double-blind study drug, then the last day of the month will be assigned to the missing day.

• If either the year is after the year of the date of the last dose of double-blind study drug or if both years are the same but the month is after the month of the date of the last dose of double-blind study drug, then the first day of the month will be assigned to the missing day.

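### SAP 5.5 anchors partial adverse event and medication dates to double-blind drug, which open-label Study 021e does not have

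*SAP*

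**What the plan says.** SAP 2.1 describes the trial in these terms: "Study 021e is a Phase 3, international, multicenter, open-label, extension study of ataluren in patients with nmCF". Any double-blind drug a patient took belongs to the preceding Study 021. Protocol 4.2 requires that treatment to be finished before entry: "Completion of study treatment (placebo or active) in the previous Phase 3, double-blind study protocol".

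The treatment-emergent window is tied to this study in both documents. SAP 4.10.1 runs it from the "first dose of study drug to 4 weeks after the last dose of study drug in this study", and Protocol 11.4.5.1 from the "first ataluren dose in this study to 4 weeks after the last ataluren dose in this study".

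The partial-date rules use a different reference:

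- **SAP 5.5.1 (adverse event onset):** "If the year is after the year of the date of the first dose double-blind study drug, then January 1 will be assigned". The same-year, same-month and later-month rules use the same anchor.
- **SAP 5.5.2.1 (medication start):** the rules again turn on cases such as "If the year of the incomplete start date is after the year of the date of the first dose of double-blind study drug".
- **SAP 5.5.2.2 (medication stop):** the anchor is the last dose of double-blind drug. If that date is missing, the instruction is to "replace it with the last visit date or data cut-off date if the subject is on-going".

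Neither document redefines the term for 021e.

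**The concern.** Every 021e patient has a real first-dose date for double-blind drug, in Study 021. A program written to the letter of SAP 5.5 would therefore run without error and return wrong dates.

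The rule is meant to give an ambiguous onset in the first-dose month or year the first-dose date, which keeps it inside the TEAE window. With an anchor 48 weeks too early, that protection is applied around the wrong date. Ambiguous onsets around the start of 021e are instead pushed to the start of the month or year, before dosing.

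The error runs one way. Affected events leave the TEAE tables and the numerator of the exposure-adjusted rate, while patient-years stay the same, so the rate can only be understated. An event is kept if worsening on treatment is recorded, because the TEAE definition also covers worsening. Total AE counts and the listings of deaths, SAEs and AEs leading to discontinuation do not depend on the window.

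Medications carry the same fault. A drug started before 021e and stopped on treatment, with a partial stop date, could be classed as prior only under SAP 4.8. That cannot happen when the last 021 dose and first 021e dose fall on the same day, and a same-day visit is the planned transition (Protocol 8.2.1).

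**Working it through.** The plan states no figure to reproduce. The check applies the SAP 5.5.1 rules under each anchor and counts imputed onsets that fall before the first 021e dose.

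**Inputs from the documents**

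| Input | Value | Source |
|---|---|---|
| First dose of first Study 021 patient | 15 Aug 2014 | Protocol 1 |
| Study 021 recruitment (estimated) | 14 months, to 15 Oct 2015 | Protocol 1 |
| Study 021 treatment | 48 weeks = 336 days | Protocol 1 |
| Termination of 021e | 2 Mar 2017 | SAP 2.1 |
| TEAE follow-up after last dose | 4 weeks = 28 days | SAP 4.10.1 |

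**Assumptions:** uniform entry to Study 021; first 021e dose = first 021 dose + 336 days + gap, with the gap 0, 14 or 30 days; constant event rate; onsets counted to 2 Mar 2017 + 28 days = 30 Mar 2017.

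**Example.** Study 021 first dose 16 Mar 2015; 021e first dose 16 Mar 2015 + 336 days = 15 Feb 2016. The true onset is 22 Feb 2016.

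| Recorded onset | Study 021 anchor | 021e anchor |
|---|---|---|
| Feb 2016 | 1 Feb 2016 (before dosing) | 15 Feb 2016 |
| 2016 | 1 Jan 2016 (before dosing) | 15 Feb 2016 |

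If both first doses fall in the same calendar year, a year-only onset goes to the Study 021 first-dose date instead of 1 January, which is still before dosing. The override that sets an imputed start back to the stop date only moves dates earlier, so it rescues nothing.

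**Which entry dates are affected.** There are 427 daily entry dates from 15 Aug 2014 to 15 Oct 2015.

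- Day missing, onset in the first-dose month: before dosing for 413 of 427 (96.7%). The 14 exceptions are first doses on the 1st of a month.
- Year only, onset in the first-dose year: before dosing for 426 of 427 (99.8%). The exception is a first dose on 1 January.
- 021e anchor: 0 of 427 in both cells.

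**Share of all TEAE onsets lost under the Study 021 anchor** = share of onsets in the cell × share of that cell lost. Cells are weighted by exposure here, so the 1st-of-month and 1 January exceptions count for more than in the date counts above.

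| Gap (days) | Year only | Day missing |
|---|---|---|
| 0 | 43.2% × 99.5% = 43.0% | 3.84% × 93.7% = 3.6% |
| 14 | 44.2% × 99.5% = 44.0% | 3.98% × 93.7% = 3.7% |
| 30 | 45.45% × 99.5% = 45.2% | 4.15% × 93.7% = 3.9% |

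Day-missing onsets in later months of the first-dose year make up 39% to 41% of all onsets, and none is lost. No loss arises outside the two cells, and none under the 021e anchor.

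**Effect on total TEAEs.** Loss = year-only share × (0.430 to 0.452) + day-missing share × (0.036 to 0.039). The shares below are illustrative and not from the documents.

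| Year only | Day missing | TEAEs lost |
|---|---|---|
| 0.5% | 1% | 0.25% to 0.27% |
| 1% | 5% | 0.61% to 0.65% |
| 5% | 10% | 2.5% to 2.7% |

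**The case against.** The strongest reply is that nobody chose this anchor. The definitions that drive the tables point correctly to this study, and SAP 5.5.2.2 allows for a patient still on treatment, which cannot describe Study 021 drug that everyone had completed. SAP 5.5.2 also mentions rescue medication ("For prior or concomitant medications, including rescue medications, incomplete (ie, partial missing) start date and/or stop date will be imputed"), which looks like another remnant. A sensible programmer would use 021e dates and lose nothing. This stands: carry-over is the likelier explanation, and the loss is zero on that reading. It does not make the text correct.

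Other points stand in part:

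- **Subject-level tables are buffered.** The main TEAE tables count a subject once per term, so a dropped event matters there only if it was the subject's sole qualifying event for that term. The event-level loss carries straight through only to the exposure-adjusted rate and the occurrence counts.
- **The percentages depend on the assumptions.** Protocol 7.1.2 contemplates gaps of more than one month. Gaps of 60 and 90 days give 47.9% and 51.0% for year-only onsets, and 4.2% and 4.6% for day-missing ones. A full 96 + 4 weeks of follow-up gives about 25% and 2.1%, but the termination date makes that unrealistic.
- **Detection is plausible.** Protocol 9.3 requires an onset date, so year-only records should be uncommon. Protocol 9.8 starts AE reporting at the first dose, so a new event dated earlier should prompt a query.
- **The silence of SAP 6 proves nothing.** It lists changes from the protocol, which has no partial-date rule to change.

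**Conclusion.** The concern holds as a minor one. SAP 5.5.1, 5.5.2.1 and 5.5.2.2 name a drug that 021e does not have, and followed as written they place some on-treatment onsets before dosing.

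The loss is zero if the programs use 021e dates. Under the literal anchor it is about 43% to 45% of year-only TEAE onsets and 3.6% to 3.9% of day-missing ones, given gaps of up to 30 days, uniform entry over 14 months, a constant event rate and counting to 30 Mar 2017. The overall effect cannot be fixed without the frequency of partial dates; 0.3% to 2.7% of TEAEs is illustrative only. No size is claimed for medications. What matters is that a derivation feeding the primary safety analysis should not depend on how a programmer reads the term.

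**What to change.** In SAP 5.5.1 and 5.5.2.1, replace the anchor with the first dose of ataluren in Study 021e. In SAP 5.5.2.2, replace it with the last dose of ataluren in Study 021e; the existing fallback for a missing last dose then makes sense. Check that the date-imputation programs use these variables.

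The cost is a phrase change in three subsections and one program check. SAP 1 allows refinement by amendment before database lock. The SAP is dated 14 July 2017, after the termination date, and the documents do not say when lock falls. If the programs already use 021e dates, no result changes. If they do not, TEAE counts rise slightly and some medications may move between prior and concomitant.

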5.5.2. Missing Date Information for Prior or Concomitant Medications

For prior or concomitant medications, including rescue medications, incomplete (ie, partial missing) start date and/or stop date will be imputed. When the start date and the stop date are both incomplete for a subject, impute the start date first.

5.5.2.1. Incomplete Start Date

The following rules will be applied to impute the missing numerical fields. If the stop date is complete and the imputed start date is after the stop date, then the start date will be imputed using the stop date.

Missing day and month

- If the year of the incomplete start date is the same as the year of the date of the first dose of double-blind study drug, then the day and month of the date of the first dose of double-blind study drug will be assigned to the missing fields.
- If the year of the incomplete start date is prior to the year of the date of the first dose of double-blind study drug, then December 31 will be assigned to the missing fields.
- If the year of the incomplete start date is after the year of the date of the first dose of double-blind study drug, then January 1 will be assigned to the missing fields.

Missing month only

• The day will be treated as missing and both month and day will be replaced according to the above procedure.

Missing day only

- If the month and year of the incomplete start date are the same as the month and year of the date of the first dose of double-blind study drug, then the day of the date of the first dose of double-blind study drug will be assigned to the missing day.
- If either the year is before the year of the date of the first dose of double-blind study drug or if both years are the same but the month is before the month of the date of the first dose of double-blind study drug, then the last day of the month will be assigned to the missing day.
- If either the year is after the year of the date of the first dose of double-blind study drug or if both years are the same but the month is after the month of the date of the first dose of double-blind study drug, then the first day of the month will be assigned to the missing day.

